5.1.5 Tables and Listings Presentation

For all analyses, summary statistics will be tabulated for the 5 following treatment groups as presented in Table 5 and corresponding to the 3 VIT-2763 cohorts, the pooling of the 2 placebo cohorts and the pooling of all VIT-2763 subjects.

Table 5 Treatment groups labels

Treatment Groups Labels	Treatment Groups Short Labels	Table order¹
Cohort 1: VIT-2763 60 mg BID	VIT-2763 60 mg BID	1
Cohort 2: VIT-2763 120 mg BID	VIT-2763 120 mg BID	2
Cohort 3: VIT-2763 120 mg TID	VIT-2763 120 mg TID	3
Cohorts 1-2-3: All VIT-2763	All VIT-2763	4
Cohort 4a/4b: Placebo	Placebo	5

¹ From left to right in statistical tables

Shorts labels will be used in tables while entire labels will be used in listings and figures for both randomized and actual treatment arms.

The listings will display all the data contained in the CRF, including the screen failure patients collected information if appropriate. The listings will be ordered by dose (from lowest to highest) and for all subjects receiving placebo (Cohorts 4a and 4b combined) and subject number.

5.1.6 Analysis Populations

The safety set will be used for all safety analyses.

The safety set excluding subjects who did not receive any dose of VIT-2763 will be used for PK concentration summary statistics analyses. PK concentration listings will be done on the ITT.

The ITT population will be used for the analysis of the primary and secondary endpoints related to haemolysis markers. These analyses will also be repeated on the PPS if it differs.

All exploratory analyses will be performed on the ITT and will be repeated on the PPS if it differs and on the mITT (except for ASCQ-Me, VOC and visceral infarctions endpoints) if applicable.

The mITT may be used depending on the number of subjects with major COVID-19 protocol deviations and the impact on analyses. The decision to use or not this population will be made prior to unblinding. In case the decision is to use mITT, all primary, secondary and exploratory endpoints tables will be repeated on mITT.

Demographics and baseline characteristics will be summarised on the safety set, ITT, and the PPS (and mITT if applicable). Medical history and concurrent medical conditions, prior and concomitant medications and procedure and study drug exposure and compliance will be described on the ITT and the PPS.

Only sets with different attributes will be presented. The enrolled or aITT populations will be used as applicable for listings except specific safety listings to be generated on safety set (see Section 5.8.1),

5.1.7 Pooling of Sites/Country

Not applicable for this study

5.1.8 Analysis of Subgroups

Not applicable for this study

5.1.9 Methods for Handling and Imputation of Missing Data

Missing and/or incomplete dates/times for AEs will be imputed in a manner resulting in the earliest onset or the longest duration during the treatment period, taking additionally into account that the start date/time should not be after the stop date/time. Stop dates/times will not be imputed if the AE is ongoing. This will be done as follows:

For a missing/incomplete start date/time the minimum of the following will be imputed:

- The maximum of the earliest possible start date/time and the date/time of first study medication administration.
- The latest possible start date/time.
- The latest possible stop date/time.

For a missing/incomplete stop date/time the maximum of the following will be imputed:

- The minimum of the latest possible stop date/time and the date/time of last study medication administration.

- The earliest possible stop date/time.
- The earliest possible start date/time.

The earliest/latest possible date is defined as:

- The date itself if it is complete.
- The date of the first/last day of the month, if month and year are available but day is missing.
- The date of the first/last day of the year, if year is available but day and month are missing. A very early/late date, e.g., 01JAN2000 (01JAN2100), if the date is completely missing.

For medications and procedures, imputation of missing or partial dates will be done to identify concomitant medications and procedures as follows:

- If the start date of the medication/procedure is unknown (i.e., complete missing date), the worst-case scenario will be assumed. The medication/procedure will be considered as both a prior medication/procedure and a concomitant medication/procedure.
- If the month and the day of the start date of the medication/procedure are missing, the month and the day will be imputed to January, 1st of the year specified.
- If the day of the start date of the medication/procedure is missing, the day will be imputed to the first day of the month specified.
- If the end date is unknown (i.e., missing), the date will be kept as missing however the medication/procedure will be considered concomitant.
- If the month and the day of the end date of the medication/procedure are missing, the month and the day will be imputed to December, 31st of the year specified.
- If the day of the end date of the medication/procedure is missing, the day will be imputed to the last day of the month specified.

For treatment group dose intake day missing (or Unknown), the day will be imputed to the end day of the previous visit.

The original incomplete, missing or partial dates and corresponding imputed dates will be presented in the listings.

During the conduct of the study, a non-neglectable number of missing data for the primary endpoint (indirect bilirubin) have been observed at baseline and Visit 6. Sensitivity analyses will be performed for the primary endpoint with different imputations for the missing data. Only missing data due to haemolysed samples will be imputed as they can be considered as missing at random while missing data because of withdrawal of the study cannot. Imputations will be as following:

- Missing baseline data will be imputed with the median of the non-missing baseline indirect bilirubin of the pooled subjects of all cohorts.
- For missing data at visit 6, 3 types of imputation will be performed: the minimal value, the mean and the maximal value within the Cohort of the subject.

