Percentages will be calculated using the total subjects per randomised treatment group, except for outputs in the PPS and the safety set, where percentages are based on the total subjects per actual treatment group.

5.1.2 *Definition of Baseline*

The baseline value for a variable will be defined as the last available (non-missing) value before the first administration of study drug. Study day 1 is defined as the day of the first study drug administration. For analysis relative day, if considered date is before the first study drug administration date, then analysis relative day will be computed as date minus first study drug administration date, otherwise, it will be computed as date minus first study drug administration date + 1.

5.1.3 *Planned Assessment Windows*

Table 4 describes the analysis visit windows (i.e. the relative study day ranges) to be applied to the assessments or sample collections dates to determine the analysis visit.

Table 4 Planned and Analysis visits Windows

Analysis Visit Label	Target Day	Planned Visit Window (Protocol Specified)	Analysis Visit Window
Baseline	1	--	Before first IMP intake
Visit 3 (Day 14)	14	± 2 days	From Day 2 to Day 21
Visit 4 (Day 28)	28	± 4 days	From Day 22 to Day 35
Visit 5 (Day 42)	42	± 4 days	From Day 36 to Day 49
Visit 6 (Day 56)	56	± 4 days	From Day 50 to Day 70
Visit 7 (Day 84)	84	± 4 days	From Day 71 and higher

Assessments (planned and unscheduled) will be re-mapped into the analysis windows. For a parameter, the following rules will be applied:

- if several assessments fall into the same analysis window, the closest to the target day will be considered for the analysis.
- When there are 2 assessments closest to the target day, the latest one will be considered for the analysis.
- if several assessments are available at the selected day, the average of the values will be taken.

In all statistical tables by visit, the analysis visits will be considered. In listings presenting data by visit, both nominal and analysis visits will be provided.

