5.7 Efficacy Analyses

5.7.1 Primary Efficacy Analysis

The changes in indirect bilirubin from baseline to Visit 6 (after 8 weeks of treatment) will be summarised using standard descriptive statistics for continuous variables with 95% confidence interval (CI) of the mean on the ITT population by randomised treatment groups as described in Table 5.

Analysis visit windows will be considered for the primary efficacy analysis (see Section 5.1.2). The analysis will be repeated on the PPS by actual treatment group and on mITT if applicable.

Three sensitivity analyses will be run on the ITT population as the primary analysis, with the imputation of the missing data due to haemolised samples at baseline or Visit 6 (see section 5.1.9). Analyses will be:

- Imputation of missing baseline with the median of the non-missing baseline of the pooled subjects. Imputation of Visit 6 missing data using the minimal value within the same cohort.
- Imputation of missing baseline with the median of the non-missing baseline of the pooled subjects. Imputation of Visit 6 missing data using mean value within the same cohort.
- Imputation of missing baseline with the median of the non-missing baseline of the pooled subjects. Imputation of Visit 6 missing data using maximum value within the same cohort.

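### The three sensitivity runs for indirect bilirubin lost to haemolysed samples never vary the baseline fill, leave Visits 3–5 unused, and count filled values as observed in the 95% CI

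*SAP*

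**What the plan says.** SAP 5.1.9 acknowledges loss of the primary endpoint at baseline and at Visit 6, large enough to call for sensitivity analyses, but gives no count. On scope it says: "Only missing data due to haemolysed samples will be imputed as they can be considered as missing at random", whereas "missing data because of withdrawal of the study cannot". The fills are:

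- Baseline: "Missing baseline data will be imputed with the median of the non-missing baseline indirect bilirubin of the pooled subjects of all cohorts".
- Visit 6: "3 types of imputation will be performed: the minimal value, the mean and the maximal value within the Cohort of the subject".

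SAP 5.7.1 repeats the same baseline rule in each of the three runs ("Imputation of missing baseline with the median of the non-missing baseline of the pooled subjects"), so only the Visit 6 fill differs. It adds: "Three sensitivity analyses will be run on the ITT population as the primary analysis". The primary summary is descriptive statistics "with 95% confidence interval (CI) of the mean on the ITT population", by the Table 5 groups: three dose cohorts, All VIT-2763, and pooled placebo. No variance correction, multiple imputation or repeated-measures model is described.

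SAP 5.1.2 takes baseline as "the last available (non-missing) value before the first administration of study drug". The schedule in SAP 2.3 (Table 3) has haemolysis markers from Visit 2 onwards, including Visits 3, 4 and 5, but not at Visit 1. SAP 5.7.3 summarises and plots the intermediate visits. SAP 3.2 makes all analyses descriptive.

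**The concern.** These runs are the only planned check on a loss of primary-endpoint data that the SAP itself acknowledges. Three features weaken them.

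1. Loss occurred at two visits, but only one fill is varied. A lost baseline has no scheduled earlier value to fall back on, so its fill matters, yet the output shows no range for it.
2. Under missing at random, the subject's own Visit 3–5 values are the natural predictors of a lost Visit 6 value. No estimate or interval for the Visit 6 change uses them.
3. A single filled value enters both n and the SD as if it had been measured, so the interval leaves out imputation uncertainty.

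A reader could take close agreement among the three runs as evidence of robustness when part of that agreement is built in.

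**Working it through.** **Inputs from the documents.** 24 subjects at 3:3:3:2:1 give 6/6/6/4/2. With placebo pooled, that is four groups of 6. No loss rate, SD or between-visit correlation is given.

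**Assumptions.** SD 1 at every visit, no treatment effect, random loss with probability p = 0.15 or 0.25 at each visit, equal between-visit correlation r = 0.6, 0.8 or 0.9. Placebo is treated as one cohort for imputation; the SAP does not say whether 4a and 4b are pooled for this.

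**Step 1: subjects with a change score.** Both visits are observed with probability (1−p)²: 0.85² = 0.7225 and 0.75² = 0.5625. Times 6, that is 4.3 or 3.4 subjects per cohort.

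**Step 2: what moves between runs.** Let a cohort of n lose k6 Visit 6 samples. The maximum-run mean change minus the minimum-run mean change is k6 × (cohort maximum − cohort minimum)/n. The number of lost baselines does not appear. If k6 = 0 the three runs are identical, however many baselines were filled.

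The chance that a cohort of 6 loses at least one baseline but no Visit 6 sample is (1 − (1−p)⁶)(1−p)⁶:

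- p = 0.15: 0.6229 × 0.3771 = 23.5%
- p = 0.25: 0.8220 × 0.1780 = 14.6%

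**Step 3: size of the omitted part.** The interquartile range of a normal variable is 1.349 SD. Moving one filled baseline in six between the quartiles shifts the cohort mean change by 1.349/6 = 0.22 SD. For comparison, one lost Visit 6 sample filled from five observed values swings it by about 2.32/6 = 0.39 SD.

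In simulation, among cohorts with any loss:

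| | 15% loss | 25% loss |
|---|---|---|
| Mean min-to-max span, planned | 0.36 SD | 0.48 SD |
| Mean span, baseline also varied between quartiles | 0.58 SD | 0.78–0.79 SD |
| Range contains the no-loss mean change, planned | 43% | 47–48% |
| Same, baseline also varied | 67% | 72% |

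**Step 4: value of the subject's own visits.** Filling Visit 6 with the mean of five cohort members has error SD √(1 + 1/5) = 1.10, whatever r is. Filling it with the subject's own Visit 3–5 mean has error SD √((4/3)(1−r)): 0.82, 0.63 and 0.37 at r = 0.5, 0.7 and 0.9.

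**Step 5: mean run against complete case.** Simulation used 10,000 trials per cell, keeping those with at least two observed changes in every cohort (9,678–9,707 at 15%; 7,687–7,799 at 25%).

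| Loss | r | Mean-run coverage, per cohort | Mean-run coverage, All VIT-2763 | Cohort RMSE, complete case | Cohort RMSE, mean run |
|---|---|---|---|---|---|
| 15% | 0.6 | 92.9% | 91.2% | 0.44 | 0.43 |
| 15% | 0.8 | 93.6% | 91.7% | 0.32 | 0.35 |
| 15% | 0.9 | 94.6% | 92.2% | 0.22 | 0.31 |
| 25% | 0.6 | 90.5% | 88.2% | 0.50 | 0.47 |
| 25% | 0.8 | 91.4% | 88.3% | 0.35 | 0.40 |
| 25% | 0.9 | 92.9% | 88.4% | 0.25 | 0.37 |

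Complete-case coverage was 94.7–95.3% throughout. Repeat simulations gave 91.2–92.4% and 87.9–89.7% in the All VIT-2763 column. Lognormal data (CV 50%) gave 91.5–92.5% and 88.1–88.9% there. At 5% loss the mean run covered 94.9–95.3% per cohort and 93.8–95.0% in the All VIT-2763 column.

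**The case against.** The strongest reply is that little rides on these runs. The primary result is unimputed, there is no hypothesis test or decision rule, and the complete-case interval performs as it should. That stands, and it limits the weight of the point.

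Other replies stand in part:

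- **Every size is assumed.** True. At 5% loss the interval problem almost vanishes. The fixed baseline fill and the unused visits do not depend on the rate.
- **The plan already shows some of this.** SAP 5.7.3 plots each subject's trajectory. The Day 50–70 window in SAP 5.1.3 could admit a repeat Visit 6 sample, and a pre-dose repeat would count as baseline. None of these yields a Visit 6 estimate or interval for a sample that stays missing.
- **Containing the no-loss mean is a criterion chosen here.** The SAP promises no such thing. The planned 43% and 47–48% also include cohorts that lost only baselines, where the range has zero width. Among cohorts that lost a Visit 6 sample, the planned range contains the no-loss mean in 58–60% and 57%.
- **The pooled column rarely coincides.** With 18 subjects, no Visit 6 loss has probability 0.85¹⁸ = 5.4% or 0.75¹⁸ = 0.6%. Identical runs are therefore a problem of the cohort columns.
- **A model on 24 subjects is a preference.** This is fair as an argument against replacing the planned runs. It does not count against a supplement.

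A reader might also infer that the imputed intervals are always too narrow. They are not. With two of six Visit 6 values lost and no baseline lost, the mean-run interval is narrower than the observed-only one at r = 0.5 (2.00 v 2.94 SD, coverage 91.3%) but wider at r = 0.9 (1.42 v 1.31 SD, coverage 95.3%).

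**Conclusion.** The point holds as a weakness of the sensitivity analyses only. That the baseline fill never varies, and that Visits 3–5 are unused, is plain from SAP 5.1.9 and 5.7.1. That filled values count as observed follows from applying the primary summary to single-imputed data with no correction.

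Under 15–25% random loss per visit, coverage of the mean run falls to about 91–92% or 88–90% in the All VIT-2763 column. Per cohort it falls by nothing to about 5 points, depending on loss and correlation. The mean run is less accurate than complete case when r is about 0.8 or more, and slightly more accurate at r = 0.6.

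Two stronger readings are not supported. One is that the primary result is compromised: it is not imputed and is unaffected. The other is that half the missing-data problem lies at baseline: the SAP gives no split by visit.

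**What to change.** In SAP 5.1.9 and 5.7.1:

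1. **Vary the baseline fill in the outer runs.** Pair the Visit 6 minimum with the pooled third-quartile baseline, and the Visit 6 maximum with the pooled first-quartile baseline. Present the result as a wider scenario range, not as strict bounds: even under random loss it misses the no-loss mean in about 27–33% of affected cohorts.
2. **Supplement the mean run with one analysis of baseline and Visits 3–6.** One option is a REML repeated-measures model with baseline as an outcome with a common mean, arm-by-visit terms, a subject random effect and an AR(1) residual. Multiple imputation from the subject's own visits is another. Report the Visit 6 mean change with its 95% CI for each Table 5 group, with and without subjects who withdrew before Visit 6, since the SAP does not regard withdrawal as missing at random.
3. **Footnote the single-imputation tables.** Say that their CIs are not nominal 95% intervals.

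The cost is SAP wording and a little programming on data already collected. The supplementary model needs a covariance form and missing at random with 24 subjects, so it should not replace the planned runs. In 24 simulated settings the REML model covered 93.9–96.3% per cohort and 93.6–96.6% in the All VIT-2763 column, with RMSE below complete case in every setting. Those settings had no treatment effect and random loss, which favours the model.

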5.2 Subject Disposition

The subject disposition data will be summarised as follows:

Number of subjects screened will be summarised overall. Number and percentage of subjects rescreened, will be also summarised overall along with number and percentage of subjects that failed screening with the reason of screen failure. This will be tabulated on the enrolled population.

Number and percentage of subjects randomised, treated, receiving a different treatment than they were randomised to and subjects that were randomised but not treated, will be summarised on the ITT by treatment group as described in Table 5.

Subjects included and excluded from safety set, ITT, PPS and mITT (in case applicable) with the reason of exclusion from any analysis set will be summarised and listed on the ITT. Subjects discontinued from treatment with reasons and who did not complete the study with reasons for discontinuations will be summarised on the ITT and listed on the aITT. Additionally, the time on study in days will be described in this table. It will be computed as the number of days from the randomisation date to the last known date of the subject in the study.

The following data will be presented in the listings:

- Date of informed consent.
- Date of randomisation.
- Date of completion/discontinuation from study
- Date of first and last intake of study medication.

Classification of protocol deviations into major and minor sponsor's definitions will be applied as per Project Specific Protocol Deviation Category List. The protocol deviations will be identified for all subjects by either site monitoring, medical review process or programming. The classification will be confirmed prior to database lock i.e. they will be classified prior to unblinding of treatment.

The number of unique subjects with at least one major protocol deviation as well as the number of subjects in each major protocol deviation category will be presented by default descriptive summary statistics on the ITT.

All protocol deviations will be listed on the aITT, including the nature of the protocol deviation, major or minor and their relation with Covid-19.

5.3 Demographics and Baseline Subject Characteristics

The following subject demographic data collected on the Demographics CRF page will be summarised:

- Sex
- Age (years)
- Age in categories for adults: <18/18-29/30-49/50-65/ >65 years
- Race: American Indian or Alaska Native/Asian/Black or African American/Native Hawaiian or Other Pacific Islander/White/Not Reported/Unknown, Other, Multiple

- Ethnicity: Hispanic or Latino/Not Hispanic or Latino/Not Reported/Unknown

The following baseline characteristics collected at screening or at baseline will be tabulated:

- Height (cm), body weight (kg), body mass index (BMI) (kg/m²) [derived as body weight / (height)²], BMI in categories for adults: <18.5/ 18.5 to <25/ 25 to <30/ ≥30 kg/m²

Heights collected in inches will be converted in cm for analysis (multiplied by 2.54). Body weights collected in lb will be converted in kg for analysis (multiplied by 0.4536).

- Aetiology of SCD collected on the Aetiology and Clinical Presentation CRF page and including underlying genotype (HbS/S or HbS/βT0), time between sickle cell disease diagnosis and informed consent (months) (derived as date of written informed consent obtained - date of sickle cell disease diagnosis / (365.25/12), number of VOC episodes within 12 months prior to screening, time between last hospitalization due to SCD and informed consent (months) (date of written informed consent obtained-derived as last hospitalization due to SCD/(365.25/12)).
- Visceral infarctions within the last 8 weeks before baseline (yes/no), number of visceral infarctions within the last 8 weeks before baseline, VOC episodes within the last 8 weeks before baseline (Yes/No), number of VOC episodes within the last 8 weeks before baseline and maximum duration of VOC episodes and maximum pain intensity in categories (0 = No pain, 1-3 = Mild pain, 4-6 = Moderate pain, 7-10 = Severe pain).

The Demographics and baseline characteristics will be summarised for the ITT, safety set, PPS and mITT (if applicable). In case some analyses sets are identical, summary statistics will not be repeated. Listings will be provided on the Enrolled Population for demographics characteristics and on aITT for baseline characteristics.

Serum virology parameters (HbsAG, HBV, HCV, HIV) and serum pregnancy test will be listed at baseline on aITT population.

5.4 Medical History and Concurrent Medical Conditions

Medical history will consist of significant conditions or diseases that stopped at or before screening. Ongoing medical conditions recorded in medical history will be considered as concurrent medical conditions. Medical history and concurrent medical conditions will be coded using MedDRA [Version 24.0]. All medical history and associated concurrent medication condition will be listed on aITT, and the number and percentage of subjects with any medical history will be summarised by SOC and PT on the ITT and PPS.

The SOC and PTs are to be sorted by decreasing order frequency of SOC and PTs in the overall subjects receiving VIT-2763. In case of equal frequency of SOC or PT, alphabetical order will be used. Subjects are included only once in each SOC and PT, even if they experienced multiple events in that SOC or PT.

